## Modified Intent-to-Treat Population (mITT) Population

The mITT population will include all subjects in the PP population plus all randomized subjects who meet all inclusion/exclusion criteria, apply at least one dose of assigned product, and return for at least one post-Baseline evaluation.

## Safety Population

All subjects who are randomized and received IP will be included in the analysis of safety.

## 7. STUDY EFFICACY VARIABLES

#### **Primary Efficacy Endpoints**

Proportion of subjects with treatment success (defined as none, minimal or mild disease, a score of 0, 1 or 2 within the treatment area) on the IGA at the Week 12 visit (Day  $85 \pm 4$  days, End of Study).

#### Secondary Efficacy Endpoints

1. Proportion of subjects with disease severity at the Week 12 visit (Day 85 ± 4 days, End of Study) consistent with none or minimal, a score of 0 or 1, within the treatment area on the IGA

AND

2. Proportion of subjects with target site plaque elevation, scaling and erythema scores of less than or equal to 1 on the PASI at the Week 12 visit (Day  $85 \pm 4$ , End of Study).

#### 8. STATISTICAL ANALYSIS METHODS

If not otherwise specified, statistical significance is defined as p<0.05 and is two-tailed. Data will be summarized with respect to demographic and baseline characteristics, efficacy variables and safety variables.

For categorical variables, the number and percent of each category within a parameter will be

4/26/2017

■ Fougera Pharmaceuticals Inc.■

calculated for non-missing data. For continuous variables with non-missing values, statistics will include number of observations, mean, standard deviation, median, minimum and maximum values.

All statistical analyses will be conducted using SAS®, Version 9.4 or higher. Datasets will be prepared using headings from Clinical Data Interchange Consortium (CDISC) Study Data Tabulation Model (SDTM) implementation for human clinical trials and ADaM (Analysis Dataset Model).

#### **8.1 Baseline Characteristics**

#### 8.1.1 Demographics Comparability of Treatment Groups

Baseline characteristics will be evaluated separately for the PP, mITT and Safety populations.

Demographic information collected at baseline includes the following:

- Age (years)
- Sex (Male/Female)
- Ethnicity (Hispanic/non Hispanic)
- Race (White, Black/African American, Native Hawaiian or Other Pacific Islander, Asian, American Indian or Alaska Native, Other)
- Baseline total BSA affected with Psoriasis
- Baseline percent BSA affected with Psoriasis
- Baseline PASI Score (the sum of the three individual component scores)
- Baseline Scores for Individual Components (Erythema, Scaling and Plaque Elevation)
- Baseline IGA Score
- Treatment location
- Treatment area size (area)
- Target lesion size (area)

Summary tables by treatment group will be presented. Continuous variables will be summarized using descriptive statistics (number of observations, median, minimum, maximum, mean and standard deviation). Categorical variables will be summarized using frequencies and percentage. Baseline treatment comparisons will be presented using Chi-Square test for the categorical variables, and Analysis of Variance (ANOVA) for the continuous variables.

All data will be listed by treatment and subject.

Tazarotene	Cream	0.05%
------------	-------	-------

Protocol /

0453-01-01/

#### 8.1.2 Medical History

At Visit 1 subjects will be questioned about their personal medical history, including psoriasis history. The medical history will include a complete review of all current diseases and their respective durations and treatments.

Medical history data will be listed by treatment and subject.

#### 8.1.3 Concomitant Medications

At Visit 1, subjects will be questioned about current and prior concomitant medication use over the 6 months. Subjects will also be questioned about ongoing or new concomitant medication use during the treatment period at Visits 2, 3 and 4.

All prior and concomitant medications taken since screening until the end of the study will be listed by treatment and subject.

#### 8.1.4 Pregnancy Test

All females of childbearing potential will have a urine pregnancy test performed at each Scheduled visit. All females of childbearing potential will have a urine pregnancy test performed at Visit 1 (Baseline), Visit 2, Visit 3, and Visit 4 (or early termination).

Pregnancy test results will be listed by treatment and subject.

#### 8.2 Primary and Secondary Endpoint Analyses

#### **Therapeutic Bioequivalence Analysis**

Therapeutic equivalence will be evaluated for both primary and secondary endpoints using the PP population, with results in the mITT population being supportive.

Based on the usual method used in OGD for binary outcomes, the 90% confidence interval for the difference in success proportions between test and reference treatment should be contained within [-0.20, +0.20] in order to establish equivalence.

The compound hypothesis to be tested is:

 $H_0: P_T - P_R < -.20 \text{ or } P_T - P_R > .20 \text{ versus}$ 

Tazarotene Cream 0.05%

Protocol /

0453-01-01/

 $H_A: -.20 \le P_T - P_R \le .20$ 

where  $P_T$  = success rate of test treatment  $P_R$  = success rate of reference treatment.

Let

 $n_T$  = sample size of test treatment group  $cn_T$  = number of patients considered as Treatment Success in test treatment group  $n_R$  = sample size of reference treatment group  $cn_R$  = number of patients considered as Treatment Success in reference treatment group  $\hat{P}_T = cn_T/n_T$   $\hat{P}_R = cn_R/n_R$ , and

$$se = (\widehat{P}_T (1 - \widehat{P}_T)/n_T + (\widehat{P}_R (1 - \widehat{P}_R)/n_R)^{1/2})$$

The 90% confidence interval for the difference in proportions between test and reference will be calculated as follows, using Yates' correction:

$$L = (\hat{P}_T - \hat{P}_R) - 1.645 \, se - (1/n_T + 1/n_R)/2$$
$$U = (\hat{P}_T - \hat{P}_R) + 1.645 \, se + (1/n_T + 1/n_R)/2$$

For the proportion of Treatment Success, if the 90% confidence interval (with Yates' Correction Factor) of the difference between the proportion of subjects considered a "treatment success" in the Test and the Reference treatment groups at Week 12 is contained within the pre-defined equivalence limits [-20%, +20%], then therapeutic equivalence will be considered to have been supported for the endpoint. The same statistical approach will be conducted for analysis of the two dichotomized secondary endpoints in the PP and mITT populations.

To declare therapeutic equivalence of the Test product to the Reference product, therapeutic equivalence must be demonstrated for only the primary endpoint in the PP population.

#### **Superiority to Placebo Analysis**

The primary measure of superiority will be evaluated using the mITT population and LOCF for missing efficacy values. The results in the PP population will be considered supportive.

The superiority of the Test and Reference products over Placebo will be concluded for the primary endpoint if the proportion of treatment success at Week 12 is statistically superior to Placebo (p < 0.05, two-sided a Cochran-Mantel-Haenszel exact test stratified by clinical site) using the mITT population and LOCF. The same statistical approach will be conducted for analysis of the two dichotomized secondary endpoints in the mITT and PP populations.

Tazarotene Cream 0.05%	Protocol /	0453-01-01/
Tazarotene Cream 0.05%	Protocol /	0453-01-01/

To declare superiority of the Test and Reference products over Placebo, their superiority must be demonstrated for only the primary endpoint in the mITT population.

A summary table with frequency and percentage of the proportion of Treatment Success by treatment group will be presented.

## **Treatment-by-Site Interaction and Pooling of Clinical Sites**

As this is a multiple-site study, the interaction of treatment-by-site may be evaluated by the Cochran-Mantel-Haenszel test (stratified by site) at the 5% significance level (p < 0.05, 2-sided) for the primary efficacy endpoint in both the PP population (for equivalence testing) and mITT population (for superiority testing).

If the treatment-by-site interaction is found to be statistically significant (p < 0.05) then the interaction will also be assessed for clinical relevance before pooling the data across sites. This will include examination of responder rates at each site where sample sizes per treatment may be influential in the assessment of the interaction.

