#### **1. INTRODUCTION**

This Statistical Analysis Plan (SAP) is based on the final Clinical Study Protocol 0453-01-01 Rev. 2 dated 12/22/2016. The SAP provides details on the planned statistical methodology for the analysis of the study data. The SAP also outlines the statistical programming specifications for the tables, listings and figures.

This SAP describes the study endpoints, derived variables, anticipated data transformations and manipulations, and other details of the analyses not provided in the study protocol. This SAP therefore outlines in detail all other aspects pertaining to the planned analyses and presentations for this study.

The following documents were reviewed in preparation of this SAP:

- Final Clinical Study Protocol 0453-01-01 Rev. 2 dated 12/22/2016
- Final eCRF Version 1.0 for

The reader of this SAP is encouraged to also read the clinical protocol for details on the conduct of this study, and the operational aspects of clinical assessments and timing for completing a subject in this study.

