## 9. TABLE, LISTING AND FIGURE SHELLS

The following shells are provided in order to provide a framework for the display of data from this study. These shells may not be reflective of every aspect of this study but are intended to show the general layout of the Tables, Listings and Figures that will be included in the final clinical study report. Tables, Listings and Figures are numbered following the ICH structure. Table headers, variables names and footnotes will be modified as needed following data analyses. All descriptive and inferential statistical analyses will be performed using SAS® statistical software Version 9.4 or higher, unless otherwise noted.

Fougera Pharmaceuticals Inc.		
Tazarotene Cream 0.05%	Protocol /	0453-01-01/

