## T16.1.9.3.1 Summary of Subjects Excluded from Efficacy Analysis (Population Determination)

		Test	Reference	Placebo	Total
Randomized	Total	XXX	XXX	XXX	XXX
Safety Population	Total	xxx	XXX	XXX	XXX
Excluded from Safety	Did not received study product	XXX	XXX	XXX	XXX
	etc.				
mITT Population	Total	xxx	XXX	XXX	xxx
Excluded from mITT	Did not received study product	XXX	XXX	XXX	xxx
	etc.				
PP Population	Total	xxx	XXX	XXX	XXX
Excluded from Excluded from PP	Restricted Medication	XXX	XXX	XXX	XXX
	etc.				

XXXX

Site

No.

XX

XX

XXX XXX

T 1	T16.1.9.3.2 Summary of Subjects Included in Analysis Population by Study Center												
		PP mITT		РР			mITT		Safety				
Name	Total Randomized	Test	Ref	Placebo	Total	Test	Ref	Placebo	Total	Test	Ref	Placebo	Total
XXXX	XXX	XXX	XXX	XXX	XXX	XXX	XXX	XXX	XXX	XXX	XXX	XXX	XXX

XXX XXX

Test: Tazarotene Cream 0.05% (Fougera Pharmaceuticals Inc.) Reference: TAZORAC® (tazarotene) Cream, 0.05% (Allergan, Inc.) Placebo: Placebo (vehicle) Cream (Fougera Pharmaceuticals Inc.)

XXX

XXX

XXX

XXX

XXX

Path: L:\Studies\_Sas\_Codes\Clinical Trial\\SAS\OUT

Created on: ddmmmyy hh:mm

XXX

XXX

Page 1 of N

XXX

XXX

(Safety Population)							
		Test	Reference	Placebo			
		(N = xxx)	(N = xxx)	(N = xxx)	P-value		
Age (years)	n	XXX	XXX	XXX	x.xxxx		
	Mean $\pm$ SD	$xx.x \pm xx.x$	$xx.x \pm xx.x$	$xx.x \pm xx.x$			
	Median	XX.X	XX.X	XX.X			
	Range	xx.x - xx.x	xx.x - xx.x	xx.x - xx.x			
Race	White	xxx (xx.x%)	xxx (xx.x%)	xxx (xx.x%)	x.xxxx		
	Black/African American	xxx (xx.x%)	xxx (xx.x%)	xxx (xx.x%)			
	Native Hawaiian or other Pacific Islander	xxx (xx.x%)	xxx (xx.x%)	xxx (xx.x%)			
	Asian	xxx (xx.x%)	xxx (xx.x%)	xxx (xx.x%)			
	American Indian or Alaska Native	xxx (xx.x%)	xxx (xx.x%)	xxx (xx.x%)			
	Other	xxx (xx.x%)	xxx (xx.x%)	xxx (xx.x%)			
Sex	Female	xxx (xx.x%)	xxx (xx.x%)	xxx (xx.x%)	x.xxxx		
	Male	xxx (xx.x%)	xxx (xx.x%)	xxx (xx.x%)			
Ethnicity	Hispanic or Latino	xxx (xx.x%)	xxx (xx.x%)	xxx (xx.x%)	x.xxxx		
	Not Hispanic or Latino	xxx (xx.x%)	xxx (xx.x%)	xxx (xx.x%)			

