## T16.1.9.7.1 Summary of Analysis Results of Primary Efficacy Endpoint Proportion of Treatment Successes on the IGA (a score of 0 or 1 or 2) at the Week 12 Visit

Equivalence: Per-Protocol Population									
	Difference								etween Treatments
Treatment Group	Number of Subjects (N)	Number of Treatment Successes (n)	Proportion of Treatment Successes (%)	Difference	90% CI Evaluation				
Test	XXX	xxx	xx.x%						
Reference	XXX	XXX	xx.x%	xx.x%	xx.x-xx.x				

Superiority: modif	Superiority: modified Intent-to-Treat Population						
		Number of	Proportion of				
Treatment	Number of	Treatment	Treatment				
Group	Subjects (N)	Successes (n)	Successes (%)	P-value			
Placebo	XXX	XXX	XX.X%				
Test	XXX	XXX	xx.x%	X.XXXX			
Reference	XXX	XXX	xx.x%	X.XXXX			

The 90% confidence interval for the difference in proportions between test and reference was calculated using Yates' correction.

Superiority of Active treatments over Placebo were tested using a two-sided Cochran-Mantel-Haenszel (CMH) exact test, stratified by clinical site, at the 5% significance level using last observation carried forward (LOCF).

Test: Tazarotene Cream 0.05% (Fougera Pharmaceuticals Inc.) Reference: TAZORAC® (tazarotene) Cream, 0.05% (Allergan, Inc.) Placebo: Placebo (vehicle) Cream (Fougera Pharmaceuticals Inc.)

Path: L:\Studies\_Sas\_Codes\Clinical Trial\\SAS\OUT

Created on: ddmmmyy hh:mm

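### The site-stratified CMH test named for treatment-by-site interaction tests the average treatment difference, not whether it varies between sites

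*SAP*

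**What the plan says.** SAP 8.2, under Treatment-by-Site Interaction and Pooling of Clinical Sites, states that "the interaction of treatment-by-site may be evaluated by the Cochran-Mantel-Haenszel test (stratified by site) at the 5% significance level". It applies this to the primary endpoint, in the PP population for equivalence and in the mITT population for superiority. Protocol 11.7 has the same sentence.

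The SAP then gives the consequence: "If the treatment-by-site interaction is found to be statistically significant (p < 0.05) then the interaction will also be assessed for clinical relevance", and "This will include examination of responder rates at each site". This precedes pooling over sites. Part of Protocol 11.7 appears to be missing from the public text, but the matching SAP paragraph reads as complete. Neither names a test of homogeneity or a treatment-by-site model term.

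The same section of the SAP makes a "Cochran-Mantel-Haenszel exact test stratified by clinical site" the main superiority analysis, and the footnote to shell T16.1.9.7.1 confirms it: "Superiority of Active treatments over Placebo were tested using a two-sided Cochran-Mantel-Haenszel (CMH) exact test, stratified by clinical site". The equivalence interval is unstratified. The only by-centre shell, T16.1.9.3.2 ("Summary of Subjects Included in Analysis Population by Study Center"), shows population counts and not success rates, although SAP 9 warns that "These shells may not be reflective of every aspect of this study".

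**The concern.** Strictly, the null hypothesis of the stratified CMH test is no association between treatment and success within any site, and its power is against an effect in a common direction. Heterogeneity between sites is a different hypothesis, and CMH is not built to detect it.

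Two wrong readings follow if the check is run as written.

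- **mITT.** A trial that wins superiority would be labelled as having a significant treatment-by-site interaction even if every site behaves alike.
- **PP.** A uniform Test–Reference difference inside the equivalence limits could get the same label, while site differences that cancel would mostly pass as no interaction. The second error matters more, because the equivalence interval pools over sites without stratification.

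**Working it through.** The plan states no figure to reproduce: assumed success rates, power and population sizes are blacked out. The check is therefore of the hypothesis tested, then of its size under stated assumptions.

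**Inputs from the documents.** Up to 855 randomized 1:1:1 gives 855/3 = 285 per arm. About 30 sites gives 285/30 = 9.5 per arm per site. The test level is two-sided 5%.

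**Formulas.** At site k let a be the successes in arm 1, n₁ and n₀ the arm sizes, m₁ and m₀ total successes and failures, and N the site total.

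- CMH = [Σ(a − E)]² / ΣV, with E = n₁m₁/N and V = n₁n₀m₁m₀/[N²(N − 1)]. Deviations are summed before squaring, so opposite signs cancel.
- Homogeneity (Breslow-Day) = Σ[(a − A)²/W], where A is the count fitted under a common odds ratio and W its variance. Deviations are squared before summing.

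**Fixed example 1: ten identical sites, 14/28 v 8/28.** E = 28 × 22/56 = 11, so each site deviates by 3. V = 28 × 28 × 22 × 34/(56² × 55) = 3.4. CMH = 30²/34 = 26.5, p = 2.7 × 10⁻⁷. The odds ratio is 2.5 at every site, so homogeneity = 0, p = 1. CMH reports an interaction where none exists.

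**Fixed example 2: five sites 18/28 v 10/28, five reversed.** Deviations are +4 and −4 and sum to 0, so CMH = 0, p = 1. The common odds ratio is 1, A = 14, W = 1/(4/14) = 3.5. Homogeneity = 10 × 16/3.5 = 45.7 on 9 df, p = 6.8 × 10⁻⁷. CMH misses a complete reversal.

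**Simulation.** Assumptions: 30 sites; 8, 9 or unequal (3–17, mean 9) subjects per arm per site; success rates as shown. There were 10,000 trials per scenario for CMH (no continuity correction), and 1,000–2,000 for Zelen's test (Monte Carlo exact, 499 draws). Ranges run over rates and site sizes.

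| Scenario | CMH flags | Zelen flags |
|---|---|---|
| mITT, active +15 points at every site (.30 v .15, .45 v .30, .60 v .45) | 91–99% | 4–6% |
| mITT, active +10 points at every site (.30 v .20, .40 v .30, .55 v .45) | 59–78% | not run |
| PP, Test −10 points at every site (Reference .45 or .60) | 59–66% | 4–5% |
| PP, 10 of 30 sites at −30 points, 20 at 0 (Reference .45 or .60) | 60–68% | 30–43% |
| PP, differences of ±10 points that cancel (mean .30–.60) | 4–5% | 15–19% |
| The same, ±15 points | 4–5% | 34–49% |
| The same, ±20 points | 4–5% | 65–82% |

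The first three rows have no interaction. Row four has the same average as row three, (10/30) × (−30) = −10 points, and CMH flags both about equally, so it cannot separate them. Of the trials in row three that still conclude equivalence, 41–55% carry a CMH flag. Under the cancelling patterns the equivalence interval succeeds with probability at least 0.994, so nothing else in the analysis would reveal the heterogeneity.

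**The case against.** **The practical harm is limited.** The check is optional, both decision rules are untouched, and a flag leads only to a look at site responder rates. In mITT the error brings extra scrutiny and a wrong label, not a missed review. All of this stands. It limits the weight of the point, but an optional test should still test what it is named for.

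**The PP figures depend on the case chosen.** SAP 5 assumes equal Test and Reference rates. With sites alike, CMH then flags about 5%, so there is no excess. At a uniform −5 points it flags 16–22% (15–20% of trials concluding equivalence). With 6 per arm per site the −10-point figure falls to 48–49%, and the share among trials concluding equivalence falls more steeply, because the wider interval then fits the limits only when the observed difference is small. This stands: the 59–66% needs a true deficit of half the margin and little attrition. It does not touch the mITT result or the failure to see cancelling effects.

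**The contrasts can be inferred.** PP is tied to equivalence and mITT to superiority, which implies Test–Reference and each active against placebo. That is a fair reading, though writing them down costs nothing.

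**Zelen's test is one choice among several.** True. Breslow-Day with Tarone's adjustment would also correct the error, and it flags more often in the non-cancelling case (39–51%). At these site sizes it is somewhat liberal: 7–8% in the uniform −10-point case, and up to 8.5% in a separate run at 9 per arm.

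**A SAP-only change would leave the SAP at odds with Protocol 11.7.** This also has force. The SAP describes itself as supplying "other details of the analyses not provided in the study protocol", but the protocol does name this test, and Amendment 2 was used to update the named superiority test in Protocol 11.6.

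**Conclusion.** The concern holds. Both documents name a test of average association as the test of interaction, and no visible text names a homogeneity test. The fixed examples show this without any assumed rates.

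The simulated sizes rest on assumed success rates, 30 sites and 8 to 9 subjects per arm per site. On those assumptions, when active is uniformly 10 to 15 points better than placebo, CMH would report an interaction in 59–99% of trials. When Test–Reference differences cancel, it would flag only at the nominal rate. In PP the false-flag problem disappears if Test and Reference are truly equal; the blindness to cancelling effects does not.

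The equivalence and superiority conclusions are unaffected. The point should be fixed because the written rule gives a wrong answer when followed and the correction is small.

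**What to change.** Before database lock, replace the test named in SAP 8.2 with wording such as:

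> Treatment-by-site interaction may be evaluated by Zelen's exact test of homogeneity of odds ratios across sites, for Test–Reference in the PP population and for Test–Placebo and Reference–Placebo in the mITT population, each at the 5% level (Monte Carlo p-value with a fixed seed if enumeration is too large).

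Keep CMH for superiority only. The site review after a flag can stay. The test needs no small-site rule, because a site with only successes or only failures contributes nothing to it. Under this wording the check remains optional.

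The SAP should say that this departs from Protocol 11.7. Protocol 11.1 allows departures from the statistical plan to be described and justified in the final report. Protocol 12.3.3 would send a protocol change to the IRB, so 11.7 can be aligned at the next amendment.

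**Cost.** One SAP sentence and a changed test call, with no new data. Whether the Monte Carlo version needs extra programming in SAS 9.4 has not been shown and should be checked first.

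**Limits to state.** Power is low for moderate heterogeneity (15–19% at ±10 points), so a non-significant result does not show consistency. Where site effects do not cancel, Zelen triggers the site review less often than CMH (30–43% against 60–68%), although the CMH flags there reflect the average difference.

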#### 8.3 Safety Analysis

All safety analyses will be based on the Safety Population.

#### 8.3.1 Adverse Events

All the adverse events (AEs) reported throughout the study will be coded and classified according to the MedDRA (Medical Dictionary for Regulatory Activities) coding dictionary (Version 18.1 or higher). Each adverse event is to be evaluated for date of start and end, seriousness, severity, relationship to the IP, action taken and outcome.

In each of the following categories, the total number and percentage of subjects with 1) at least one AE, 2) discontinued study drug due to AEs, 3) AE severity and AEs related to the IP, 4) serious AEs and death will be summarized separately by treatment groups.

A summary table of the number and percent of subjects with AEs by system organ class, preferred term, and treatment group will be presented. Each subject will be counted only once within each preferred term.

Tazarotene Cream 0.05%	Protocol /	0453-01-01/
------------------------	------------	-------------

A frequency summary table of the number of AEs by system organ class, preferred term, severity, and treatment group will be presented. Severity will be classified as "Mild", "Moderate", or "Severe".

Similarly, a frequency summary table of the number of AEs by system organ class, preferred term, and relationship to the IP, and treatment group will be presented. Relationship to a study drug will be classified as "Suspected" or "Not Suspected".

Should sufficient data exist, adverse event frequencies will be compared between treatments using Fisher's exact test.

